1 STUDY SYNOPSIS

Complete Protocol Title	Clinical Evaluation Of Vanguard Deep Dish Rotating Platform Knee
Protocol Number	BMETEU.CR.EU13B
Short Protocol Title	Vanguard Deep Dish
Sponsor	Biomet GS CC bv [name]
Manufacturer	Biomet Inc.
Study Device(s)	Vanguard DDRP Vanguard CR
Study Objectives/Endpoints	
Primary Endpoint American Knee Society Knee Score at 2-year post-operative.
 
Secondary Endpoint
 
- Patient success at 2 years postoperative- American Knee Society Score at each postoperative visit.- Radiographic evaluation at each postoperative visit.- Adverse events.- Survivorship at 10 year postoperative.
Indications/Target Population	Patients which are candidates for a total knee replacement because of gonarthrosis
Inclusion/Exclusion Criteria	
Inclusion criteria
 
1. Patients with a pre-operative knee score of < 70.2. Patients scheduled to undergo primary total knee replacement with any of the following indication:
a. Painful and disabled knee joint resulting from osteoarthritis.b. One or more compartments are involved.3. Need to obtain pain relief and improve function.4. Ability and willingness to follow instructions, including control of weight and activity level, and to return for follow-up evaluations.5. A good nutritional state of the patient.6. Full skeletal maturity of the patient, patients who are at least 18 years of age.7. Patients of either sex.8. Consent form read, understood, and signed by patient. 
Exclusion criteria
 
Absolute contraindications include the following diagnoses:
 
a. Patients with a pre-operative knee score of >70.b. Infection.

	
c. Osteomyelitis.d. Previous partial or total prosthetic knee replacement on the operative side.e. Skeletal immaturity of the patient, patients who are less than 18 years of age.f. Sepsis.g. Patients who had body mass index >40.
Study Design	International, multicenter, randomised, controlled trial
Clinical Phase	Post-market
Sample Size	A total of 340 study subjects implanted with the study device per cohort.
Length of Study	13 years (3 years of enrollment (all sites) and 10 years of follow-up)
Materials and Methods	Case report forms were completed in hospital at Pre-op, Surgery, Immediate post-op, and the 6 week, 6 months, 1-year, 2-year, 3-year, 5-year, 7-year, and 10-year intervals visits.
Data Collection	Paper
Statistical Reporting	Data collected was summarized and reported to each participating investigator. Statistical analysis was conducted by Zimmer Biomet. Survivorship was evaluated using Kaplan-Meier.
Scores/Performance Assessments	Knee Society Score, Oxford Knee Score, WOMAC, Forgotten Joint Score and Lower Extremity Activity Scale.
Standards	
The PMCF is compliant with the below:
 
• ISO 14155: 2020 - Clinical investigation of medical devices for human subjects - Good clinical practice. (*) The study protocol may have been drafted according to another version of the ISO 14155. Adverse Event definitions and reporting are according to ISO 14155:2020.• The Declaration of Helsinki (DoH) - Ethical principles for medical research involving human subjects.
Study Funding	Funding for this clinical study is made available by Zimmer Biomet to support clinical data collection, IRB/EC review fees and other expenses associated with the conduct and execution of this study protocol as outlined in the fully executed Clinical Trial Agreement.

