2.2 Statistical Analysis

2.2.1 Descriptive statistics

Continuous outcome variables and their differences are analyzed with parametrical statistical techniques, such as t-tests, unless the normality assumption does not seem reasonable for the data, in which case non-parametric techniques are considered e.g. Wilcoxon/Mann-Whitney tests.

Categorical outcome variables are analyzed with chi-square tests and/or Fisher's exact tests (depending on the expected values in the categories). For the relevant parameters (subsidence, survival pain and function) also the 95 percent confidence intervals are calculated.

The effect of parameters such as age, sex and operators are evaluated using multiple variate analysis.

All data are analyzed by blinded researchers.

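### No rule covers knees revised before a radiographic visit, so by default the comparison to 10 years understates a difference in loosening or subsidence

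*Combined protocol and SAP*

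**What the plan says.** Section 1 (Study Synopsis), under Study Objectives/Endpoints, makes "Radiographic evaluation at each postoperative visit" a secondary endpoint. Ten-year survivorship and adverse events are separate secondary endpoints. Materials and Methods in the same section schedules "6 week, 6 months, 1-year, 2-year, 3-year, 5-year, 7-year, and 10-year intervals visits".

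Section 2.2.1 assigns methods by type of variable. "Continuous outcome variables and their differences are analyzed with parametrical statistical techniques, such as t-tests", with rank tests as the fallback when normality is doubtful. "Categorical outcome variables are analyzed with chi-square tests and/or Fisher's exact tests", depending on expected counts. It adds: "For the relevant parameters (subsidence, survival pain and function) also the 95 percent confidence intervals are calculated". Subsidence is the only radiographic-type parameter named anywhere. For covariates: "The effect of parameters such as age, sex and operators are evaluated using multiple variate analysis", with no model given.

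The only time-to-event method is under Statistical Reporting in Section 1: "Survivorship was evaluated using Kaplan-Meier". It is not linked to the radiographic endpoint.

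The documents do not define radiographic failure or an analysis set for the films. They do not say how the repeated films are to be compared, or how a knee revised earlier, a death or a missing film is handled.

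**The concern.** Once a study component has been taken out, later films cannot show it loosening or subsiding. If the tests in 2.2.1 are run on whatever films exist at a visit, a knee revised for loosening or subsidence is absent from every later comparison. It is absent because of the finding being compared. This differs from ordinary loss to follow-up, and the 15% allowance in Section 2.1 does not help: it restores numbers, not comparability.

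After the first such revisions, the comparison at a given visit is between selected knees, not between the randomised arms. The result then depends partly on how often each arm revises its failed knees. Section 2.2.2 foresees publishing 2-, 5- and 10-year results, so a reader could take similar late radiographic tables as reassurance that they do not give.

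**Working it through.** **The plan's own figures.** None bears directly on this point. The arm size used below comes from Section 2.1: 127/(1 − 0.15) = 149.4, rounded up to 150; 150 + 20 = 170 per arm; 2 × 170 = 340. This agrees with the plan.

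**Assumed inputs.** The documents give no loosening or revision rates. Let p be the true cumulative proportion of knees loosened by 10 years, and r the share of those already revised. Other exits (death, loss, revision for other reasons) are taken as unrelated to loosening, and an unrevised loosened knee is taken to show it on the film.

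**Formula.** Of all knees, p(1 − r) are loosened and in place, and 1 − pr are in place. The 10-year films therefore show p(1 − r)/(1 − pr).

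**Same revised share in both arms, p = 8% against 4% (true gap 4.0 points):**

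| r | Worse arm | Better arm | Gap (points) |
|---|---|---|---|
| 30% | 0.056/0.976 = 5.74% | 0.028/0.988 = 2.83% | 2.9 |
| 60% | 0.032/0.952 = 3.36% | 0.016/0.976 = 1.64% | 1.7 |
| 90% | 0.008/0.928 = 0.86% | 0.004/0.964 = 0.41% | 0.45 |

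The worse arm still looks worse in each row, and the ratio stays near 2. What is lost is the absolute difference and the power to see it.

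**Different revised shares.** With 80% revised in the worse arm and 30% in the better, the films show 0.016/0.936 = 1.71% against 2.83%: the order reverses. With the better arm at r = 50%, its films show a = 0.02/0.98 = 2.04%. Equality needs r = (0.08 − a)/(0.08(1 − a)) = 0.0596/0.0784, about 76% in the worse arm. The distortion can also run the other way. With 30% revised in the worse arm and 80% in the better, the films show 5.74% against 0.008/0.968 = 0.83%, a gap of 4.9 points, larger than the truth.

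**Power.** For a two-sided 0.05 test with 170 per arm, power = Φ((Δ − 1.96·SE₀)/SE₁), with SE₀ pooled and SE₁ unpooled. Counting all loosened knees, 8% against 4% gives 34%. With half the loosened knees revised in each arm, the films show 4.17% against 2.04% among 163.2 and 166.6 knees, and power is 20%.

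**Other assumed rates, half revised in each arm:**

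| True rates | Gap, true → films (points) | Power, all knees → films | Share revised in worse arm for equality (better arm 50%) |
|---|---|---|---|
| 12% vs 6% | 6.0 → 3.3 | 49% → 29% | about 77% |
| 10% vs 5% | 5.0 → 2.7 | 42% → 24% | about 76% |
| 8% vs 4% | 4.0 → 2.1 | 34% → 20% | about 76% |

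**Do the other endpoints fill the gap?** Read survivorship in the ordinary way, as freedom from revision. At 8% against 4% with half revised, it sees 4% against 2% revised for loosening, and the films see 4.17% against 2.04%. Each shows about half the true gap, and no stated analysis adds them. In the reversal case, survivorship sees 0.08 × 0.8 = 6.4% against 0.04 × 0.3 = 1.2%, while the films point the opposite way.

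**The case against.** The strongest reply is that the plan is silent here and that a silence is being read as a method. That is partly right. A reader might infer that the plan restricts the comparison to knees still in place and tests the arms visit by visit. No section says so. The list in 2.2.1 is open-ended, and it adds confidence intervals and an unspecified multivariable analysis. Neither loosening nor revision is mentioned. What stands is that the endpoint is set at each visit, the named tests have no time structure, and a removed component yields no later film. Dropping the knee is therefore what happens unless a rule prevents it.

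A second reply is that device failure is captured elsewhere. It is: revisions reach the trial through ten-year survivorship and adverse events, so they are not lost. But survivorship counts removed knees and the films count knees in place, and nothing combines the two.

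A third reply is that the endpoint is secondary and unpowered, and its tests sit under a heading of descriptive statistics. This is fair. Even with every loosened knee counted, power is only 34% at 8% against 4%. That limits what any radiographic test can show, and it is a reason to report an interval for an interpretable quantity. It does not justify leaving the quantity dependent on revision practice.

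**Conclusion.** The concern holds as a gap with a predictable consequence. Without a rule for revised knees, the later radiographic comparison loses failed knees because they failed. With similar revised shares in the two arms, an absolute difference in loosening is understated: roughly halved when half the failed knees have been revised, and nearly gone when 90% have. The same mechanism applies to subsidence, which was not computed separately. All rates are assumptions, and the size in this trial cannot be known from the documents.

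Two stronger readings are not supported:

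- A reader might infer that the arm with more failures will look equal or better. That needs a clearly larger revised share in that arm (about 76% to 77% against 50% for equality) or near-complete revision in both. The general effect is attenuation.
- A reader might infer that the trial's non-inferiority conclusions are tilted. Section 2.1 confines that test to the primary endpoint and one secondary endpoint, and the two it sizes are the Knee Society Score and 2-year patient success. The radiographic endpoint has no stated non-inferiority test or margin.

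This is worth correcting because the fix is cheap. It does not threaten the main result.

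**What to change.** In Section 2.2.1:

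- Define radiographic failure before the arms are unblinded.
- Count revision for loosening or subsidence as failure on the date of revision.
- Report the cumulative incidence of first failure by arm, with the difference and 95% confidence interval at 2, 5 and 10 years. Treat death and revision for other reasons as competing events.
- Keep the per-visit radiographic tables as description, and show beside each visit, by arm, the number already revised and the number still in place.

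The cost is SAP wording and one further analysis, with no extra visits. There are three limits. A single failure definition has to be agreed. The reason for revision must be available from the revision or adverse event records, which the documents do not confirm. Failures that are not revised can be dated only to the interval between visits, and these widen to two or three years late in follow-up.

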2 STATISTICAL ANALYSIS PLAN

2.1 Sample Size

Patient populations for RCT group and NRCT group are determined based on non-inferiority test. Furthermore, non-inferiority is tested for both the primary endpoint and one of the secondary endpoints. Sample size calculation is conducted for each endpoint. The final patient number is the larger of the two sample sizes.

Endpoint – American Knee Society Score (KSS)

N=67 Correction for 15% Lost to Follow-up (approximately 7.5% each year): N=79

Endpoint: Patient success rate at 2 year postoperative:

N=127, Correction for 15% Lost to Follow-up (LTf) (approximately 7.5% each year): n=150

The final patient population is the larger of these two sample sizes. Therefore, 150 cases are needed each arm. To compensate for possible lost to follow up add 20 more patients each arm, hence, the total number of cases for RCT group is 340.

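### Does the sample size correct twice for loss to follow-up, so that 340 contradicts the stated 15% loss?

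*Combined protocol and SAP*

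**What the plan says.** Section 2.1 sizes the trial on two non-inferiority comparisons and takes the larger result.

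- Knee Society Score, the primary endpoint: "N=67 Correction for 15% Lost to Follow-up (approximately 7.5% each year): N=79".
- Patient success at 2 years, a secondary endpoint: "N=127, Correction for 15% Lost to Follow-up (LTf) (approximately 7.5% each year): n=150".

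The second is larger, and the section concludes: "Therefore, 150 cases are needed each arm". The next sentence reads "To compensate for possible lost to follow up add 20 more patients each arm", and from this "the total number of cases for RCT group is 340". The section gives no rate, time horizon or further reason for the 20. The figure of 170 per arm is not printed; it is 150 + 20. The synopsis repeats the 340.

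**The concern.** The 150 per arm already contains the whole allowance for 15% loss, yet 20 more per arm are added under the same label. The final number then seems to rest on a loss rate that the plan does not state. A reader cannot tell whether the sponsor expects 15% of 2-year outcomes to be missing, or something nearer 25%.

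Two things would be at stake. If 15% is right, the trial enrols more patients than its own calculation requires. If a much higher loss is really expected, the 15% understates the missing data in a non-inferiority comparison, where missing outcomes can blur a true difference between the arms.

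**Working it through.** **Inputs, all from section 2.1.** Evaluable patients per arm before loss: 67 (Knee Society Score) and 127 (patient success). Loss by 2 years: 15%. Later addition: 20 per arm. Total: 340. Equal allocation is implied, because one number is given for each arm.

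**1. Reproduce the first correction, N / (1 − loss).**
- 67 / 0.85 = 78.8, rounded up to 79. Matches.
- 127 / 0.85 = 149.4, rounded up to 150. Matches.

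Other conventions do not give both figures. Multiplying by 1.15 gives 77.05 and 146.05, rounded up to 78 and 147. Compounding 7.5% a year (1 − 0.925² = 14.4%) gives 78.3 and 148.4, rounded up to 79 and 149. The 150 is therefore the full simple correction for 15%.

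**2. Reproduce the total.** 150 + 20 = 170 per arm; 2 × 170 = 340. Matches.

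**3. Is the 20 a second 15% correction?** 150 / 0.85 = 176.5, rounded up to 177. It is not; that would have added 27 per arm. The 20 looks like a round number.

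**4. What loss can 170 per arm absorb?**
- Patient success: 1 − 127/170 = 25.3%.
- Knee Society Score: 1 − 67/170 = 60.6%.

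**5. Size of the excess.** With one correction the total is 2 × 150 = 300. 340 − 300 = 40, and 40/300 = 13.3%.

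**6. Evaluable patients if loss is 15%.** 170 × 0.85 = 144.5 per arm, against 127 needed.

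**7. Effect on power for patient success.** The document gives neither alpha nor power, so both are assumed here. With z_a and z_b the normal quantiles for one-sided alpha and planned power, power at 144.5 per arm is Φ[(z_a + z_b) × √(144.5/127) − z_a], where √(144.5/127) = 1.067.

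| Assumed planned power | One-sided alpha 5% | One-sided alpha 2.5% |
|---|---|---|
| 80% | 84.3% | 84.8% |
| 90% | 93.0% | 93.3% |

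In every case power rises by 3 to 5 percentage points.

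**The case for a change.** The strongest case for a change is that the text does not call the 20 a safety margin. It gives loss to follow-up as the reason, and the lines just above had already quantified that and corrected for it. The 340 is a headline figure, carried into the synopsis, and it cannot be derived from the stated assumptions alone. One clause would settle the matter.

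The repetition is real, and so is the missing rationale. The inference that the 15% and the 340 are incompatible does not stand. A plan may expect 15% and still recruit a margin in case loss is worse, and the wording allows this: 150 are described as needed, and the 20 are set against loss that is possible. The 25.3% is what enrolment could tolerate; nothing in the document says it is expected, so there is no ground for saying that the 15% understates missing data.

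A second reading is also open. The 15% is a 2-year figure, whereas the synopsis lists 10-year survivorship as a secondary endpoint and schedules visits at 3, 5, 7 and 10 years. The 20 may have been meant for later loss, although section 2.1 does not say so.

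Rewriting the section around 25% would do harm, because the printed steps from 67 to 79 and from 127 to 150 both rest on 15%. Deleting the sentence about the 20 would remove the only explanation of how 150 per arm becomes 340 in total.

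**Conclusion.** No change to the plan is called for. Each printed number follows from the one before it. The only gap is that the 20 per arm has no stated rate or horizon, and a reader fills it sensibly as a margin beyond the expected 15%.

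The cost is at most 40 patients over 300. The synopsis requires patients to be already scheduled for a primary total knee replacement, so these 40 would not be having an operation they otherwise would not need. The gain is tolerance of up to 25.3% loss before the success comparison falls below 127 per arm, or about 144 evaluable per arm if loss is 15%. The primary endpoint needs only 67 per arm and is secure on either reading. Recruiting more patients does not weaken a non-inferiority test at a fixed margin and alpha. Restating the reason would leave enrolment, analysis and conclusions as they are.

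This rests on taking 67 and 127 as given. They cannot be checked, because the document prints no margin, standard deviation, success rates, alpha or power; that is a separate matter. The power figures above are illustrations under assumed values, and the conclusion does not depend on them.

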2.2 Statistical Analysis

2.2.1 Descriptive statistics

Continuous outcome variables and their differences are analyzed with parametrical statistical techniques, such as t-tests, unless the normality assumption does not seem reasonable for the data, in which case non-parametric techniques are considered e.g. Wilcoxon/Mann-Whitney tests.

Categorical outcome variables are analyzed with chi-square tests and/or Fisher's exact tests (depending on the expected values in the categories). For the relevant parameters (subsidence, survival pain and function) also the 95 percent confidence intervals are calculated.

The effect of parameters such as age, sex and operators are evaluated using multiple variate analysis.

All data are analyzed by blinded researchers.

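### Non-inferiority is declared for 2-year KSS and one secondary endpoint, but the analysis section gives only general difference tests, and no margin, alpha, sidedness or decision rule is stated

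*Combined protocol and SAP*

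**What the plan says.** Section 2.1 builds the trial on non-inferiority: "Patient populations for RCT group and NRCT group are determined based on non-inferiority test". It adds that "non-inferiority is tested for both the primary endpoint and one of the secondary endpoints". The synopsis names the American Knee Society Knee Score (KSS) at 2 years as primary and lists 2-year patient success first among the secondary endpoints. Section 2.1 sizes both. Patient success drives the total: "N=127, Correction for 15% Lost to Follow-up (LTf) (approximately 7.5% each year): n=150". A further allowance follows: "To compensate for possible lost to follow up add 20 more patients each arm". That gives 170 per arm.

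Section 2.2.1, headed as descriptive statistics, describes the analysis in general terms. For continuous data: "Continuous outcome variables and their differences are analyzed with parametrical statistical techniques, such as t-tests". If normality is doubtful the text continues "in which case non-parametric techniques are considered e.g. Wilcoxon/Mann-Whitney tests". For categorical data: "Categorical outcome variables are analyzed with chi-square tests and/or" Fisher's exact tests, depending on expected counts. It also provides 95% confidence intervals for subsidence, survival, pain and function, and a multivariable analysis of age, sex and operator. Section 2.2 never mentions non-inferiority.

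**The concern.** A non-inferiority test needs a margin, an error rate and a rule for deciding. The documents print none of these. The listed tests, run as they usually are, ask whether the arms differ from zero. A non-significant answer does not show that a deficit beyond some margin has been excluded. The tests could be run against a margin-shifted null, but that needs the missing margin. The 95% intervals do not close the gap, because they are not compared with a margin and patient success is not among the items listed.

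At stake is the trial's main conclusion. With no rule fixed, the 2-year claim depends on how a difference test happens to be read.

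**Working it through.** **1. The plan's own figures.** The loss-to-follow-up arithmetic reproduces: 67/0.85 = 78.8, so 79; 127/0.85 = 149.4, so 150; 2 × (150 + 20) = 340. The base values 67 and 127 cannot be reproduced, because margin, alpha, sidedness, power, SD and success rates are not given.

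**2. Inputs.** From section 2.1: N=67 (read as per arm, like the success figure) and N=127 per arm; 170 per arm with 15% loss, so 170 × 0.85 = 144.5, taken as 144 evaluable. Assumed, because the documents are silent: one-sided alpha 2.5% or 5%, power 80% or 90%, control success 80-95%, and no true difference at the sizing stage. The margins below are back-calculated for illustration only and are not candidates for adoption.

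**3. Implied margins.**
- KSS: margin/SD = (z_α + z_β) × √(2/67). The z sums are 2.486, 2.802, 2.926 and 3.242 for 5%/80%, 2.5%/80%, 5%/90% and 2.5%/90%. This gives 0.430, 0.484, 0.506 and 0.560 SD.
- Success: margin = (z_α + z_β) × √(2p(1−p)/127). The smallest is 2.486 × √(2 × 0.95 × 0.05/127) = 0.068. The largest is 3.242 × √(2 × 0.80 × 0.20/127) = 0.163.

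**4. Success, true deficit equal to the margin, 144 per arm.** The probability of a two-sided chi-square p > 0.05 was found by summing exact binomial probabilities over all outcome pairs, and likewise for a Wald confidence limit at the paired alpha.

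| Alpha/power | Margin, points (p = 0.95 to 0.80) | Chi-square p > 0.05 | Wald limit excludes margin |
|---|---|---|---|
| 5%/80% | 6.8-12.5 | 32-45% | 5.08-5.80% |
| 2.5%/80% | 7.7-14.1 | 23-36% | 2.55-3.11% |
| 5%/90% | 8.0-14.7 | 19-33% | 5.01-5.76% |
| 2.5%/90% | 8.9-16.3 | 13-25% | 2.47-3.04% |

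Hand check of the upper end (p = 0.95, 5%/80%): success in the other arm is 0.950 − 0.068 = 0.882 and pooled success is 0.916. The pooled SE is √(2 × 0.916 × 0.084/144) = 0.0327 and the unpooled SE is 0.0324. Then Φ((1.96 × 0.0327 − 0.068)/0.0324) = Φ(−0.12) = 0.45; the exact value is 0.451. The lower end, exact, is 0.126.

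The smallest ratio of the chi-square rate to alpha in the table is 19.4%/5% = 3.9.

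**5. KSS, true deficit equal to the margin, 144 per arm.** From the noncentral t distribution with noncentrality margin/√(2/144), p > 0.05 occurs in 4.72%, 1.64%, 1.03% and 0.27% of trials, in the scenario order of step 3. The paired alphas are 5%, 2.5%, 5% and 2.5%, so none is exceeded. The reason is that KSS alone needs 67 per arm and the trial is much larger.

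**6. Sensitivity.** If only 127 per arm are evaluable (a loss of 1 − 127/170 = 25.3%, beyond the planned 15%), chi-square p > 0.05 occurs in 17.0-49.5%. KSS then reaches 7.35% and 2.99% in the two 80%-power scenarios, above their alphas of 5% and 2.5%. With 70% control success and 144 per arm, the lowest chi-square rate is 9.8%.

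**The case against.** The strongest reply is that section 2.2.1 prescribes no wrong test. Its wording is illustrative, it states no null hypothesis, and the named tests can be shifted to a margin. This stands in part: the fault is one of omission, and the harm needs a misreading that no passage endorses. But a shifted test cannot be run without a margin, so the declared hypothesis still has no stated test.

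The public text may also be condensed: it prints N=67 and N=127 without inputs, and the synopsis describes the analysis in the past tense. A reader might infer that the sponsor never set a margin. The documents do not support that; they show only that none is stated here.

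Other stronger readings also go too far:
- *Fisher's test would make matters worse.* Section 2.2.1 ties the choice of test to expected counts. Even with 127 per arm, the mean expected failures are at least 10.7 per arm in every scenario with 80-95% control success. Under the conventional threshold of 5 (an assumption), Fisher's test would rarely be triggered.
- *Either endpoint alone could carry the claim, raising total error.* Section 2.1 says both are tested, and the synopsis ranks them. Nothing suggests that one suffices.
- *A KSS result that is significantly worse yet non-inferior shows a flaw.* A correct confidence-limit rule can produce the same pair of findings.
- *The primary endpoint is badly exposed.* At the planned 15% loss it is not, under the assumed inputs.

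**Conclusion.** The point holds and must be fixed. The declared non-inferiority hypotheses for 2-year KSS and patient success have no margin, alpha, sidedness or decision rule, and the listed tests in their usual form do not test them. That conclusion rests on the text alone.

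The numerical harm is conditional on p > 0.05 being read as non-inferior and on the assumed inputs. It mainly concerns patient success, where false claims would be about 13-45% at 144 per arm instead of roughly the nominal level. For KSS the misreading does not exceed alpha at 144 per arm, and does so at 127 only in the 80%-power scenarios.

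**What to change.** In section 2.2.1, for the two 2-year non-inferiority endpoints:

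1. Specify a confidence interval for the between-arm difference: the mean difference for KSS, and the risk difference for success by a score-type method such as Miettinen-Nurminen or Newcombe. The Wald limit reached 5.8% at a nominal 5% in the check, so it is not the best choice. Conclude non-inferiority only if the unfavourable limit excludes the margin used to derive N=67 or N=127.
2. State that margin, the alpha and the sidedness, taken from the sizing records. If no record made before the data were seen exists, report estimates with confidence intervals and make no confirmatory non-inferiority claim.
3. If KSS is not normal, use an interval for the mean difference (for example bootstrap) in place of the Wilcoxon test for this endpoint, so that the margin keeps its scale.
4. Test KSS first and success second, in line with their primary and secondary ranking.
5. State that a non-significant difference test is not evidence of non-inferiority.

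The general tests can stay for the other outcomes. The cost is a little SAP wording and analysis work; no new patients or data are needed. The real downside is that the non-inferiority claim may be lost if no margin was recorded.

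### The analysis section does not tie the promised non-inferiority test of 2-year KSS to a between-arm difference, a confidence interval or a margin, and does not name pre-operative KSS as a covariate

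*Combined protocol and SAP*

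**What the plan says.** The synopsis names the Knee Score at 2 years as the primary endpoint and requires a pre-operative knee score below 70 for entry. I take these to be the same score and call it KSS.

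SAP section 2.1 states that "non-inferiority is tested for both the primary endpoint and one of the secondary endpoints". For KSS it gives "N=67 Correction for 15% Lost to Follow-up (approximately 7.5% each year): N=79". The success-rate endpoint needs more patients (127, or 150 after the same correction) and sets the size: "Therefore, 150 cases are needed each arm". A further 20 per arm brings the randomised group to 340.

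SAP section 2.2.1 is the only text on analysing continuous outcomes. Its content on this point is:

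- Main method: "Continuous outcome variables and their differences are analyzed with parametrical statistical techniques, such as t-tests".
- Fallback: "unless the normality assumption does not seem reasonable for the data, in which case non-parametric techniques are considered e.g. Wilcoxon/Mann-Whitney tests".
- Intervals: "For the relevant parameters (subsidence, survival pain and function) also the 95 percent confidence intervals are calculated".
- Covariates: "The effect of parameters such as age, sex and operators are evaluated using multiple variate analysis".
- Blinding: "All data are analyzed by blinded researchers".

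The section does not mention non-inferiority, KSS, a between-arm contrast or a margin.

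**The concern.** A non-inferiority conclusion needs three things stated together: the quantity compared, its confidence interval (or an equivalent shifted test), and the margin. Section 2.1 announces the hypothesis, and section 2.2.1 lists families of tests. No sentence joins them for 2-year KSS, so a reader cannot tell from the plan which result would count as success.

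Two gaps follow. First, the usual form of a t-test asks whether the difference is zero, and failing to reject that does not establish non-inferiority. The rank fallback is further away. As described it yields no mean difference, and the trigger for using it is a judgement about normality with no stated rule. Second, the trial holds a baseline measurement of its primary outcome for every eligible patient, yet the plan does not say that it will be used. Adjusting for it would give a somewhat narrower interval for almost nothing.

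**Working it through.** **1. The plan's own figures.** Dividing by (1 − 0.15): 67/0.85 = 78.8, rounded up to 79; 127/0.85 = 149.4, rounded up to 150. Then 150 + 20 = 170 per arm and 2 × 170 = 340. These steps reproduce. The base figure of 67 cannot be checked, because the margin, SD, alpha and power are not in the text supplied.

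**2. Evaluable numbers at the planned size.** At 15% loss, 170 × 0.85 = 144.5, taken as 144 per arm. The 127 per arm required for the success rate corresponds to 25% loss (127/170 = 0.747). Only 67 evaluable would mean 61% loss (67/170 = 0.394). The synopsis words its total of 340 as per cohort. If that meant per arm, 340 × 0.85 = 289 would be evaluable and the risks below would be smaller.

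**3. An illustrative margin.** Assume 67 is per arm and the true difference is 0. The normal approximation is margin/SD = √(2/67) × (z for alpha + z for power). With one-sided 0.025 and 80% power this is 0.1728 × (1.960 + 0.842) = 0.484; the noncentral t gives 0.488. Other noncentral t values are 0.564 (0.025, 90%), 0.432 (0.05, 80%) and 0.508 (0.05, 90%). The documents do not say which applies, so the margin cannot be recovered from the sample size. I use 0.488 SD as the base case.

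**4. Two decision rules compared.** The 95% CI half-width is h = t × √(2/n), in SD units. A two-sided t-test against zero is non-significant if the observed deficit is below h. Non-inferiority is shown if the deficit is below 0.488 − h. The last column is the chance that the t-test against zero is non-significant when the true deficit equals the margin.

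| Evaluable per arm | h: non-significant below | Non-inferior below | Chance non-significant |
|---|---|---|---|
| 127 | 0.247 | 0.240 | 2.8% |
| 144 | 0.232 | 0.256 | 1.5% |
| 67 (not the planned size) | 0.342 | 0.146 | 20.0% |

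At 127 the two cut-offs are almost equal. At 144 the test against zero is slightly the stricter rule.

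**5. Power without adjustment.** In the base case it is 97.2% at 127 and 98.5% at 144 per arm. Over the four combinations in step 3 it runs from 96.3% to 99.8%.

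**6. Gain from adjustment.** Relative to the unadjusted 2-year comparison, ANCOVA shortens the CI by 1 − √(1 − ρ²), where ρ is the correlation between pre-operative and 2-year KSS. The documents give no ρ. For assumed values of 0.2, 0.3, 0.4 and 0.5 the reduction is 2.0%, 4.6%, 8.3% and 13.4%. At 127 per arm the half-width of 0.247 SD becomes 0.247 × 0.980 = 0.242 at ρ = 0.2 and 0.247 × 0.866 = 0.214 at ρ = 0.5.

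**The case against.** The strongest reply is that the two SAP sections should be read together. Section 2.1 sets a non-inferiority hypothesis and section 2.2.1 supplies the test family. A t-test shifted by the margin is equivalent to the CI rule, and section 2.2.1 states no null hypothesis of zero difference. This stands: the plan is compatible with a correct analysis. What remains is that it does not require one.

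A reader might go further and infer that the sponsor means to treat a non-significant difference as proof of non-inferiority. No sentence says so. A reader might also take the 20% figure as the trial's risk. It applies only if 67 per arm were evaluable. That is the KSS requirement before the loss correction, and the larger endpoint overrides it.

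Other wording helps the plan in part. The mention of differences could mean between-arm differences or changes from baseline. The interval sentence covers pain and function, which may overlap with KSS content, but it names neither KSS nor an arm contrast. The covariate list is open, so baseline KSS is not excluded, but that sentence concerns the effects of covariates and not an adjusted treatment effect. Blinded analysis limits selective choice of test; it does not define the quantity tested. Rank methods are only to be considered, and a rank test can also be shifted by a margin, though the plan does not say that it will be.

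Finally, adjustment can be called a preference. The unadjusted randomised comparison is valid and, on the assumptions above, well powered. That is right, and adjustment is the smaller part of the point.

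**Conclusion.** The point holds as a gap in specification with a cheap and better alternative. The plan promises a non-inferiority test of 2-year KSS, but the analysis section ties neither the t-test nor the rank fallback to a between-arm KSS difference, a CI or a margin, and it does not name the available baseline score as a covariate. It does not show that a wrong analysis was planned, that the unadjusted comparison is invalid, or that power is short.

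At the planned size the numerical consequence is small: a 2.8% to 1.5% chance of the misreading at 127 to 144 evaluable per arm, and a CI 2 to 13% narrower with adjustment. The first range rests on a margin of 0.49 SD inferred from an assumed per-arm reading of 67, true difference 0, one-sided 0.025 and 80% power. The second rests on an assumed correlation of 0.2 to 0.5. The case for change is mainly that the primary conclusion should follow from a written rule. This is a change the sponsor should make; it does not undermine the trial.

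**What to change.** In SAP section 2.2.1, make the primary analysis of 2-year KSS an ANCOVA on arm and pre-operative KSS. Report the adjusted between-arm mean difference with its CI, and conclude non-inferiority only from that CI against the margin used for the sample size, at the matching confidence level. If residuals are skewed, use a robust or bootstrap CI for the same mean difference and keep Wilcoxon/Mann-Whitney as a sensitivity analysis. If the sponsor prefers no adjustment, the minimum is the unadjusted 2-year mean difference with its CI, judged against the margin in the same way.

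The cost is a few sentences and a little analysis time. No new data are needed, because the pre-operative score decides eligibility and a pre-operative form is completed. The synopsis describes data collection and analysis in the past tense. If the 2-year analysis is already done, add this one as a labelled post hoc analysis beside the reported result.
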